## STUDY PROTOCOL

### Infusion:

- 3% NaCl Hypertonic Saline
- Furosemide & 3% NaCl Hypertonic Saline

### Diet:

- Low salt (2.6g NaCl/day, 1 g Na+)
- High salt (18g NaCl/day, 7 g Na+)

**Figure 1. Study Design**

All subjects will complete 8 visits (see above). Visits 1, 3, and 4 will be at the UD Center for Biomedical and Brain Imaging (CBBI). Visits 2, and 5-8 will take place at UD's Science, Technology & Advanced Research (STAR) Campus.

### VISIT 1: INFORMED CONSENT, CBBI (60 MINUTES)

Informed consent will be obtained in person by a trained member of the research team at CBBI. All procedures and aspects related to the study including any potential risks will be described to the subject. The subject will read the informed consent form and the investigator will answer any questions that the subject may have prior to obtaining the subject's written consent. As documentation of the informed consent the subject and the investigator performing the consent will sign the consent document. A copy of the signed consent form will be given to the subject. After giving consent, subjects will lie in the mock scanner for at CBBI to screen for claustrophobia. Lastly, subjects will be given a personal food information form and 3-day diet recall to record food intake (2 weekdays and 1 weekend). These will help our dietician prepare food for the controlled feeding portion of this study. Subjects must complete these forms before the Nurse Managed Primary Care Center screening (visit 2). Subjects will not be excluded for food allergies

[figure not shown]
or preferences, but we will exclude individuals with very specific dietary restrictions such as celiac disease, gluten sensitivity, if an individual is vegan, or indicates an eating disorder. We can accommodate vegetarians who eat dairy and eggs.

### **VISIT 2: SCREENING, STAR CAMPUS (60 MINUTES)**

All participants will be screened at the Nurse Managed Primary Care Center in the Health Sciences Complex of STAR. This initial screening visit lasts approximately 1 hour and involves answering an MRI screening form and a medical history questionnaire. Additionally, nurses will assess resting blood pressure, 12-lead electrocardiogram, height and weight, and obtain a venous blood and urine sample. The blood and urine sample will assess liver and kidney function, a lipid profile (i.e., cholesterol), a complete blood count, glucose, sodium, potassium, and chloride. Approximately 2 teaspoons of blood will be sampled. Investigators will review all information. Individuals with any signs or symptoms of disease (example: history of angina, chest pain, dizziness, or shortness of breath, etc.) will be excluded. Individuals with blood work within normal limits, and a resting electrocardiogram within normal limits will be accepted into the study. The results from the screening are reviewed by the registered nurse to determine if participants qualify for the study. Participants will receive a copy of the data collected on their vital statistics. Women taking hormonal or non-hormonal contraceptives will not be excluded. Additional exclusion criteria include allergy to sulfa drugs (Lasix/furosemide), claustrophobia, low blood pressure (systolic blood pressure <100mmHg and/or diastolic blood pressure <60 mmHg), high blood pressure (defined here as systolic blood pressure >130mmHg and/or diastolic blood pressure >80 mmHg), low potassium levels in the blood (<3.5 mmol/L), a history of cancer, diabetes, or any other chronic disease; a history of any heart disease; use of tobacco or nicotine products; nursing mothers; or a body mass index less than 18.5kg/m^2 or greater than 30kg/m^2. Certain medications may also result in exclusion from participating; this will be determined by the NMPCC in consultation with the primary investigator on an individual basis. If one of the test results is abnormal, individuals will be referred to their personal provider.

### VISITS 3 & 4: fMRI SCAN (2 hours/visit; CBBI)

Subjects will be asked to log food and water intake for the 3 days leading up to the MRI visits on the AHA Sodium Tracker. Subjects will be asked to consume a diet containing 2,300 mg of sodium each of these days. Subjects will consume their own food. Food will NOT be provided by the dietitian for the 3 days leading up to the MRI visits. Subjects will be instructed to refrain from taking over the counter medications for 48 hours, and from vigorous aerobic exercise or alcohol for 24 hours prior to MRI scans. Subjects will come into the study visit after at least a four-hour fast. The MRI studies must be completed within 3 months of the screening. If we are unable to schedule both MRI visits within 3 months of screening, subjects will be asked to come to the Cardiovascular Physiology Lab again before the MRI visit for a blood draw to check if electrolyte levels are normal. The second MRI data collection must be performed no sooner than 1 week from the first MRI data collection.

**Figure 2: Timeline of Experimental Protocol**

#### ***Urine Sample Collection and Absorbent Brief or Condom Catheter (men only)***

All subjects will be asked to provide a urine sample. We will measure electrolytes, osmolality, and specific gravity as well as perform a pregnancy test for women. Only women with a negative pregnancy test will be allowed to continue with the study. If the test is positive, the participant will be informed and referred to their primary care

provider. After subjects provide a urine sample, they will be asked to change into scrubs and put on the absorbent brief, both provided by the research team in a private changing room and bathroom. Subjects will be asked to urinate into the brief when they have the urge to urinate during the MRI. Male subjects will have the additional option of wearing a condom catheter instead of the absorbent brief. Likewise, male subjects will be asked to urinate while wearing the condom catheter when they have the urge to urinate during the MRI.

### ***Catheter Insertion & Blood Sample***

At CBBI, a registered nurse will insert one catheter into the arm of the participant, leaving a small flexible tube in their vein prior to the MRI scan. The catheter will be used for infusion of the saline and furosemide, and to draw blood samples. Blood samples will be obtained pre- and post-infusion to measure electrolytes, osmolality, hematocrit, and hemoglobin. Some of the blood sample will be stored in our -80C freezer (indefinitely) for future assessment of renin angiotensin aldosterone system hormones, inflammatory markers, and reactive oxygen species. About 40 mL of blood will be sampled from the intravenous catheter, pre- and post-infusion (80 mL total). The catheter will be removed at the end of the study.

### ***Furosemide Administration***

Each subject will undergo two separate MRI study visits (visit 3 and visit 4), one with and one without NKCC2 antagonism. Furosemide (NKCC2 antagonist) will be purchased through the Nurse Managed Primary Care Center from Heritage Pharmaceuticals through McKesson ([link here](#)). NKCC2 antagonism will be achieved by administering a bolus of furosemide (40mg in 4mL of 0.9% NaCl isotonic saline) over a 2-minute period immediately prior to the hypertonic saline infusion. This timing will achieve peak NKCC2 blockade. A bolus of 0.9% NaCl (4mL) will be administered over a 2-minute period during the control infusion, and the participant will be blinded to the condition. A registered nurse, under the off-site supervision of a cardiologist will administer the bolus of furosemide and administer the hypertonic saline infusion.

### ***Hypertonic Saline Infusion***

A 3% NaCl hypertonic saline will be infused at a rate of  $0.15 \text{ ml} \cdot \text{kg}^{-1} \cdot \text{min}^{-1}$  into the participant's arm for 30 minutes total while participants are in the MRI scanner. The hypertonic saline will be purchased from a manufacturer and will be prepared by the registered nurse. The volume of hypertonic saline in the tubing will be closely monitored by the registered nurse to ensure that participants are receiving the correct amount of saline. The volume infused and infusion rate is similar to previous studies infusing saline, which we have previously published (Farquhar et al AJP-Heart 2006). The 3% hypertonic saline is expected to raise blood sodium concentration and plasma osmolality approximately 1-2%. Blood samples will be taken pre- and post-infusion to measure changes in blood sodium concentration and osmolality.

***MRI Scan.*** The MRI scan will take approximately 1 hour (Figure 2). The subject will be free to stop at any time, either by indicating their desire to do so directly to the investigator or by squeezing a ball while in the MRI scanner that alerts the technologist who is running the machine.

- ***MRI Screening Form.*** Participants will again fill out the MRI screening form prior to the scan to ensure they can safely undergo MRI.
- ***Structural and BOLD MRI.*** During all scans the subjects will wear disposable earplugs and headphones to reduce scanner noise. Participants may also be asked to wear a pulse oximeter on their finger to measure heart rate or a respiratory belt around their chest to measure breathing. Both devices are provided by Siemens with the MRI scanner, are MR-safe and MR-compatible, and interface with the MRI scanner software. Participants will also wear an FDA-approved MRI compatible blood pressure cuff on their middle finger throughout the scan that measures blood pressure through a Pulse Decomposition Analysis. This device is made through BioPac Systems and is MR-safe and MR-compatible.

## **OPTIONAL COMPONENT OF STUDY (VISITS 5-8)**

### **VISITS 5 & 7: BLOOD DRAW, URINE COLLECTION, BP; & FOOD & EQUIPMENT**

#### **PICKUP, STAR (30min/visit)**

Salt Sensitivity Assessment: Subjects will consume a low (2.6g NaCl/day, 1g Na+) and high (18g NaCl/day, 7g Na+) sodium diet for 7 days each (randomized, washout between diets). Twenty-four-hour BP (SunTech Oscar2) and urine, to confirm diet compliance, will be collected on day 8 of each diet week (Figure 2). A change of 24 hr mean BP of > 5 mmHg, from the low to the high sodium condition will be considered a salt sensitive response.

Participants will report to the CV lab of STAR on day 1 (Figure 1) of each randomized diet to 1) have a venous blood draw performed on them by a research team member trained in phlebotomy; 2) provide a urine sample; 3) have brachial blood pressure measured; and 4) pick up food, a 24hr BP cuff, and urine collection supplies. Blood samples will be obtained to measure electrolytes, osmolality, hematocrit, and hemoglobin. Some of the blood sample will be stored in our -80C freezer (indefinitely) for future assessment of renin angiotensin aldosterone system hormones, inflammatory markers, and reactive oxygen species. About 40 mL of blood will be collected from the butterfly needle insertion. Urine samples will be obtained to measure electrolytes, osmolality, and specific gravity as well as a pregnancy test for women. Diets will be prepared by a registered dietician on staff. These diets will be separated by a minimum 4-week washout, but no greater than 6 months. Participants will drink water ad libitum but quantities will be recorded. Participants during different dietary control phases may be provided with Gatorade, juices and milk; in addition, the dietician will provide a detailed diet menu to allow for additional beverages such as coffee, decaffeinated coffee and/or tea that will not be provided to the participants. Physical activity will also be assessed using a physical activity monitor to evaluate activity patterns during each period of the controlled feeding study. Prior to starting the controlled salt diet, we will confirm that all female subjects are not pregnant by performing an over-the-counter pregnancy test. To accomplish this, participants will have to provide a small urine sample.

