## **VISITS 6 & 8: BLOOD DRAW, URINE COLLECTION, BP; & EQUIPMENT DROP-OFF, STAR (30min/visit)**

Participants will report to the CV lab of STAR on day 9 (Figure 1) of each diet to 1) have a venous blood draw performed on them; 2) provide a urine sample; 3) have brachial blood pressure measured; and 4) drop off any left over food, the 24hr BP cuff, accelerometer and urine collection supplies. Blood samples will be obtained to measure electrolytes, osmolality, hematocrit, and hemoglobin. Some of the blood sample will be stored in our -80C freezer (indefinitely) for future assessment of renin angiotensin aldosterone system hormones, inflammatory markers, and reactive oxygen species. About 40 mL of blood will be collected from the butterfly needle insertion. Urine samples will be obtained to measure electrolytes, osmolality, and specific gravity as well as a pregnancy test for women.

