**Seven-day diets:**

There are minimal risks associated with consuming a 7-day low salt diet and 7-day high salt diet. During the high salt diet, blood pressure may rise to higher-than-normal levels, and subjects might experience slight hand swelling, frequent urination from increased water intake, bloating, nausea and/or vomiting during the dietary salt manipulation. There is no increased risk for women regardless of phase of menstrual cycle and diets should not affect menstruation.

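### Does the day-8 blood pressure and urine collection fall outside the seven-day controlled diet?

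*Combined protocol and SAP*

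**What the plan says.** The Salt Sensitivity Assessment paragraph under Visits 5 & 7 describes a low and a high "sodium diet for 7 days each (randomized, washout between diets"). The Seven-day diets paragraph of the risk section repeats the duration: "consuming a 7-day low salt diet and 7-day high salt diet".

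The timing statements are:

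- Pick-up (Visits 5 & 7): "Participants will report to the CV lab of STAR on day 1 (Figure 1) of each randomized diet".
- Pregnancy test (same section): "Prior to starting the controlled salt diet, we will confirm that all female subjects are not pregnant".
- Measurement (same section): 24-hour blood pressure and "urine, to confirm diet compliance, will be collected on day 8 of each diet week".
- Return (Visits 6 & 8): "Participants will report to the CV lab of STAR on day 9 (Figure 1) of each diet", when they "drop off any left over food, the 24hr BP cuff, accelerometer and urine collection supplies".

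The measurement serves two purposes. The urine checks compliance. The pressure classifies participants: "A change of 24 hr mean BP of > 5 mmHg, from the low to the high sodium condition" counts as a salt-sensitive response. No sentence gives the first or last fed day, or the clock time at which the 24-hour collections start.

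**The concern.** Taken literally, a seven-day diet whose day 1 is the pick-up visit ends on day 7. A collection on day 8 would then be made while participants eat their own food.

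If intake became similar after the two diets, the sodium contrast between them would shrink during the very window used to measure it. The compliance urine would understate adherence, and the pressure difference would be pulled towards a classification of not salt sensitive. A measurement taken on the wrong day cannot be repaired in the analysis, so the question deserves a check.

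**Working it through.** **Does one schedule satisfy every statement?** The protocol's own figures are a diet of 7 days, pick-up on day 1, measurement on day 8 and return on day 9.

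| Reading | Fed days | Number of fed days | Is day 8 fed? |
|---|---|---|---|
| Labels count fed days from pick-up | 1 to 7 | 7 | No |
| All labels taken as diet days | 1 to 9 | 9 | Yes, but contradicts the stated 7 |
| Labels count visit days, feeding starts the day after pick-up | 2 to 8 | 8 − 2 + 1 = 7 | Yes, the last fed day |

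The third reading meets every stated number. Three details favour it, though none proves it:

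- The return visit is called day 9 of the diet. No seven-day diet has a ninth fed day, so the label must count visit days. The day-1 label has the same form and cites the same figure.
- The urine pregnancy test belongs to the day-1 visit and precedes the start of the diet, so day 1 cannot be a full fed day.
- Leftover food is returned on day 9, the morning after a day-8 finish on this reading.

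**How much of the 24-hour window is covered?** Take a diet of 7 × 24 = 168 h and a 24-hour window starting on day 8 at 00:00, 08:00 or 09:00. These clock times are assumptions, since the protocol gives none.

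| Assumed start of diet | Hours of the window on the diet |
|---|---|
| Day 1, 00:00 | 0 of 24 |
| Day 1, after the visit (09:00 to 17:00) | 0 to 17 of 24 |
| Day 2, 00:00 or 08:00 | 15 to 24 of 24 |

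The 15 h figure pairs a diet ending at midnight after day 8 with a window starting at 09:00. The 24 − 15 = 9 uncovered hours run from midnight to 09:00 on day 9, when little is normally eaten.

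**What would be lost if day 8 were unfed?** The planned contrast is (7 − 1) g of sodium; 6 / 22.99 = 0.261 mol, or 261 mmol/day. Suppose intake becomes equal on day 8, excretion adapts exponentially with half-life h days, and pressure follows in proportion. The mean contrast retained over 24 h is (1 − e^(−k))/k, with k = ln 2 / h.

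| Assumed h (days) | Retained | Contrast (mmol) | True 6 mmHg reads | True 10 mmHg reads | Smallest true response reading 5 mmHg |
|---|---|---|---|---|---|
| 0.5 | 0.541 | 141 | 3.2 | 5.4 | 5 / 0.541 = 9.2 |
| 1 | 0.721 | 188 | 4.3 | 7.2 | 5 / 0.721 = 6.9 |
| 1.5 | 0.801 | 209 | 4.8 | 8.0 | 5 / 0.801 = 6.2 |

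Even then, only true responses between 5 mmHg and the last column would change class.

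**The case for a change.** The strongest case for a change is that the reconciling schedule is written nowhere, while the pick-up visit is expressly called day 1 of the diet. Staff who followed that phrase literally could supply food for days 1 to 7 and measure on day 8, and the salt-sensitivity result depends wholly on that window. The sentence fixing day 8 also cites Figure 2, which the MRI section captions as the timeline of the experimental protocol, so that cross-reference may not help. Clarifying would cost one sentence.

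Part of this stands. The prose does not put diet days and collection days on one explicit count, and the Visits 5 & 7, Visits 6 & 8 and Seven-day diets texts would need to be reconciled for a reader to be certain. What does not stand is the step from an unstated start day to a biased measurement. That step requires reading the day-1 label as a fed day while ignoring that the day-9 label cannot be one. It also sets aside Figure 1, the study-design figure that both labels cite.

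The claim that compliant participants would look non-compliant is weaker still. The protocol sets no urinary threshold, and the least favourable assumption above leaves a contrast of 141 mmol.

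**Conclusion.** No change to the plan follows. The stated numbers fit a schedule in which day 8 is the seventh and last fed day, and the purpose given for the urine, confirming compliance, makes sense only if the team regards day 8 as part of the diet. The unstated first fed day is a gap in wording that those running the feeding would be expected to fill sensibly, and Figure 1 may already fill it.

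The attenuation of 20% to 46% (1 − 0.801 to 1 − 0.541) is conditional on food stopping after day 7, intake becoming equal at once, an assumed half-life of 0.5 to 1.5 days and a proportional pressure response. The documents support none of these, so it is not an estimate of bias in this study.

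The consequences are also contained. Visits 5 to 8 are headed as optional, and the Statistical Analysis section models functional connectivity by infusion phase and furosemide condition without a salt-sensitivity variable. The conclusion rests on the day labels being visit-calendar counts. If Figure 1 showed feeding on days 1 to 7 with collection on day 8, the concern would be real for the optional component, though still not for the connectivity analysis.

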## **VISITS 6 & 8: BLOOD DRAW, URINE COLLECTION, BP; & EQUIPMENT DROP-OFF, STAR (30min/visit)**

Participants will report to the CV lab of STAR on day 9 (Figure 1) of each diet to 1) have a venous blood draw performed on them; 2) provide a urine sample; 3) have brachial blood pressure measured; and 4) drop off any left over food, the 24hr BP cuff, accelerometer and urine collection supplies. Blood samples will be obtained to measure electrolytes, osmolality, hematocrit, and hemoglobin. Some of the blood sample will be stored in our -80C freezer (indefinitely) for future assessment of renin angiotensin aldosterone system hormones, inflammatory markers, and reactive oxygen species. About 40 mL of blood will be collected from the butterfly needle insertion. Urine samples will be obtained to measure electrolytes, osmolality, and specific gravity as well as a pregnancy test for women.

### **Alternate order of MRI (Visits 3 and 4) and Salt Sensitivity Testing (Visits 5-8).**

Subjects will be given the option to instead do the salt sensitivity testing (visits 5-8) first, followed by the MRI study visits (visits 3 and 4) if they have previously volunteered in an MRI study at the University of Delaware (and were not claustrophobic) or must begin with the salt sensitivity testing due to the logistics of scheduling.

## **STUDY POPULATION AND RECRUITMENT**

We will recruit 50 normotensive men and women (18-45 years old), from the community surrounding the University of Delaware. Our study sample will be representative of the general population, including all races/ethnicities. Our strategies will include: Nextdoor app, classifieds, flyers posted locally, and targeted social media ads using 'bump' advertisement. The study will include all healthy participants with blood pressure between 100/60 to 130/80 mmHg. Individuals will not have any chronic diseases.

Participants excluded from the study will include individuals with known cardiovascular disease, high blood pressure (defined here as systolic blood pressure >130mmHg and/or diastolic blood pressure >80 mmHg), low blood pressure (defined here as systolic blood pressure <100mmHg and/or diastolic blood pressure <60 mmHg), an

allergy to sulfa drugs (Lasix/furosemide), low potassium in the blood (hypokalemia, <3.5 mmol/L), metabolic diseases, cancer, kidney disease, a body mass index (BMI) outside of the range of 18.5 and 30 kg/m^2, nicotine product consumer, pregnant or planning to become pregnant, and other chronic diseases. Participants with any conditions which would contra-indicate MRI: implant of pacemakers or pacemaker wires; artificial heart valve; brain aneurysm surgery; middle ear implant; non-removable hearing aid or jewelry; braces; cataract surgery or lens implant; implanted mechanical or electrical device; foreign metallic objects in the body such as bullets, BBs, shrapnel, or metalwork fragments; claustrophobia; uncontrollable shaking or the inability to lie still for 1.5 hours will be excluded.

## **RISKS AND BENEFITS**

There are no known risks associated with obtaining height, weight, resting blood pressure, or urine analysis to test for pregnancy.

### Catheter Insertion & Butterfly Needle Insertion for Blood Draw

Participants may have pain or bruising at the site where the catheter or butterfly needle is placed in the arm, and there is a small risk of infection. Fainting sometimes occurs during or shortly after blood is drawn.

### Condom Catheter

The condom catheter is secured on the male penis by a self-adhesive latex. The self-adhesive latex may increase male participant discomfort when removing the condom catheter. Additionally, there is a risk of an allergic reaction to the latex if male participants are allergic to latex.

